3.1.1. Adverse Events

An adverse event is considered a Treatment-Emergent Adverse Event (TEAE) if the event started during the effective duration of treatment. All events that start on or after the first dose of study intervention, but before the end of the study will be flagged as TEAEs. The algorithm will not consider any events that started prior to the first dose date.

3.1.2. Clinical Safety Laboratory Tests

Safety laboratory tests will be performed as described in the protocol.

The investigator must review the laboratory report, document this review, and record any clinically significant changes occurring during the study in the AE section of the CRF.

Clinically significant abnormal laboratory test findings are those that are not associated with the underlying disease, unless judged by the investigator to be more severe than expected for the participant's condition.

Baseline will be the last pre-dose measurement in each study period. Change from baseline (CFB) will be calculated for all post-baseline timepoints.

To determine if there are any clinically significant laboratory abnormalities, the hematological, clinical chemistry (serum) and urinalysis safety tests will be assessed against the criteria specified in the sponsor reporting standards. The assessment will take into account whether each participant's baseline test result is within or outside the laboratory reference range for the particular laboratory parameter.

3.1.3. Vital Signs

Single supine blood pressure will be measured at screening, follow-up visit and early termination (ET; if applicable). Triplicate supine measurements will be taken at all other times as specified in the Schedule of Activities (SoA) of the protocol. The average of the triplicate measurements will be calculated prior to analyzing the data. Respiratory rate, pulse rate and temperature will be measured at each timepoint specified in the protocol.

Baseline for these measures will be defined as the last pre-dose measurement in each study period.

The following endpoints will be determined:

- Change from baseline in systolic and diastolic BP, pulse rate, temperature, and respiratory rate
- The minimum and maximum post-dose systolic and diastolic BP, pulse rate, temperature, and respiratory rate
- The maximum increase and decrease from baseline over all measurements taken postdose for systolic and diastolic BP, pulse rate, temperature, and respiratory rate values

The maximum increase from baseline will be calculated by selecting the maximum CFB over the respective period, except in the case where a participant does not show an increase. In such an instance, the minimum decrease should be taken. Similarly, the maximum decrease from baseline will be determined by selecting the minimum value of the CFB. In cases where a participant does not show a decrease, the minimum increase should be taken.

3.1.4. Continuous Cardiac Monitoring

Continuous cardiac monitoring will be performed using telemetry as outlined in the protocol.

All abnormal rhythms will be recorded and reviewed by the study physician for the presence of rhythms of potential clinical concern. The time, duration, and description of the clinically significant event will be recorded in the CRF.

Events deemed of clinical concern will be recorded as AEs and will be summarized as part of the standard AE outputs.

3.1.5. 12-Lead ECG

A single 12-lead ECG will be obtained on all participants at screening, follow-up visit and at ET (if applicable). 12-lead ECGs will be recorded in triplicate at all other times as specified in the the protocol. The average of the triplicate readings collected at each assessment time will be calculated for each ECG parameter. If one or two of the triplicates are missing, the non-missing values will be used for the average, and missing values will not be imputed.

The mean of the three averages of *the triplicate ECG measurements collected at -1.0, -0.5, and 0 hours pre-dose on Day 1 of each period will serve as each participant's baseline value for that period.* If one or two of the averages are missing, the non-missing averages will be used for the mean, and missing values will not be imputed.

ECG endpoints include heart rate, QT interval, PR interval and QTcF and QRS complex. If not supplied QTcF will be derived using Fridericia's heart rate correction formula:

QTcF (msec) = QT (msec) / (RR)^{1/3}, where RR (sec) = 60/Heart Rate (if RR not provided).

The following endpoints will be determined:

- Change from baseline in QT, QTcF, PR, QRS interval and heart rate
- The maximum post-dose QTcF, heart rate, PR and QRS interval
- The maximum increase from baseline over all measurements taken post-dose for QTcF, heart rate, PR and QRS values

The maximum increase from baseline will be calculated by selecting the maximum change from baseline over the respective period, except in the case where a participant does not show an increase. In such an instance, the minimum decrease should be taken.

3.1.6. Physical Examinations

Complete physical examinations will be conducted at screening or upon admission for a participant's first period in the study. At all other timepoints, a brief physical exam may be performed for the findings during a previous exam or new/open AEs at the investigators discretion. Height and weight will only be measured at the screening visit.

Physical examination findings collected during the study will be considered source record and will not be required to be reported, unless otherwise noted.

Any untoward physical examination findings that are identified during the active collection period and meet the definition of an AE or SAE will be summarized as part of the standard AE output.

3.1.7. Neurological Examinations

Neurological examinations may be conducted by a physician, trained physician's assistant, or nurse practitioner as acceptable according to local regulation at the nominal time points

specified in the SoA. The neurological exam will consist of assessment of higher cortical function, the cranial nerves, motor function, deep tendon reflexes, sensory exam, and coordination and gait. Additional neurological examinations that are outside of SoA (eg, to evaluate an AE) may be conducted at the discretion of investigator. All neurological exams should be done to the extent needed to assess the participant for any potential changes in neurological status, as determined by the investigator (or designee). Changes in the timing or addition of timepoints for the neurological examinations may occur based on emerging data.

Any untoward findings identified on neurological examinations, conducted during the active collection period will be captured as AEs or SAEs, if those findings meet the definition of an AE or SAE, and will be summarized as part of the standard AE outputs.

3.2. Secondary Endpoint(s)

Blood samples for PK analysis of PF-07293893 will be taken according to the SoA in the protocol. *The plasma PK parameters for PF-07293893, following oral dose administration, will be derived from the plasma concentration-time profiles using standard noncompartmental methods as detailed in Table 2, as data permit.* Table 2 also shows the analysis scale and method for each parameter.

In all cases, actual PK sampling times will be used in the derivation of PK parameters. If actual PK sampling times are not available, nominal PK sampling times will be used in the derivation of PK parameters.

The following plasma PK parameters as described in Table 2 will be determined.

Table 2. Plasma PF-07293893 PK Parameters

Parameter	Definition	Method of Determination	Analysis Scale	PF-07293893
AUC_{last}	Area under the plasma concentration-time profile from time 0 to the time of the last quantifiable concentration (C_{last})	Linear/Log trapezoidal method	ln	D, A
AUC_{inf}^*	Area under the plasma concentration-time profile from time 0 extrapolated to infinite time	$AUC_{last} + (C_{last}^* / kel)$, where C_{last}^* is the predicted plasma concentration at the last quantifiable timepoint estimated from the log-linear regression analysis	ln	D, A

C_{max}	Maximum plasma concentration	Observed directly from data	ln	D, A
T_{max}	Time for C_{max}	Observed directly from data as time of first occurrence	R	D
$t_{1/2}^*$	Terminal elimination half-life	$\log_e(2)/kel$, where kel is the terminal phase rate constant calculated by a linear regression of the log-linear concentration-time curve. Only those data points judged to describe the terminal log-linear decline will be used in the regression.	R	D

Key: ln=natural-log transformed, R=raw (untransformed),
 D=displayed with descriptive statistics,
 A=analysed using a statistical model (for evaluating food effect)
 *=if data permit

T_{last} will also be provided as a support parameter for AUC_{last} . T_{last} values will only be listed and not summarized.

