4.2. Scientific Rationale for Study Design

The population planned for this study will be healthy male and female participants. Female participants will be confirmed to be of non-childbearing potential, since at the present time embryo-fetal developmental toxicity studies with PF-07293893 have not been conducted. In male participants, appropriate measures are expected to be followed to minimize potential transfer of PF-07293893 via semen to partners (see [Appendix 4](#)).

Given this is the first time PF-07293893 will be administered to humans, an escalating single oral dose crossover design with careful assessment and ongoing review of safety, tolerability and PK data of PF-07293893 is planned. Due to the findings of transient clinical signs of cardiovascular and neuropulmonary effects in the non-clinical chronic toxicology studies, neurological examination, RR and body temperature measurement will be performed in this study. In addition, a precautionary sentinel dosing will be used. The highest anticipated C_{max} and AUC_{24} of PF-07293893 will not exceed the pre-defined human exposure stopping limits. Furthermore, to permit an unbiased assessment of safety, the participants' treatment assignments (active treatment versus placebo) will be blinded to both site staff (except those involved in preparation of doses) as well as the study participants. However, to permit real-time review of the safety and PK data, a limited number of sponsor study team members will be unblinded (see [Section 6.4.3](#)).

In each period, approximately 6 participants are planned to receive PF-07293893, and 2 participants are planned to receive placebo. The 4-period crossover design will permit both within and between participant assessment of safety/tolerability and PK at multiple dose levels and placebo. An additional cohort may be included if, based on emerging data from the first 2 cohorts, it is deemed necessary to meet the objectives of this study. For a given participant, dosing will be separated by at least 7 days. This planned dosing interval is deemed sufficient based on the projected PF-07293893 terminal half-life (see [Section 4.3.1](#)).

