4.3.3. Human Exposure Stopping Limits

The NOAEL in the 1 month GLP toxicity study in mice (the most sensitive species) was 100 mg/kg/day (CCl ██████████). Therefore, the mouse NOAEL exposures are used to set human exposure limits for PF-07293893.

After correcting for species-dependent, plasma protein binding between mouse and human ($f_{u,p}$ of CCl ██████████ respectively):

- The human PF-07293893 C_{max} limit is a total C_{max} of CCl ██████████ ng/mL (CCl ██████████ ng/mL unbound).
- The human PF-07293893 AUC_{24} limit is a total AUC_{24} of CCl ██████████ ng•h/mL (CCl ██████████ ng•h/mL unbound).

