4.3.4. Rationale for Dose Selection

The safety, tolerability, and plasma PK of PF-07293893 after administration of single escalating oral doses across a wide dose/exposure range will be evaluated in this study. The doses presented in Table 3 are projected based on nonclinical data and may be modified based on emerging observed human safety, tolerability, and PK data generated during this study. The initial range of planned doses in this study were established using toxicokinetic data, predicted human PK parameter estimates, and projected efficacious concentrations.

Table 3. Predicted Human Exposures and Safety Margins at Proposed Single Doses of PF-07293893

Dose (mg)	Projected Exposures ^a		Safety Margins ^b	
	C_{max} (ng/mL)	AUC_{24} (ng•h/mL)	C_{max}	AUC_{24}
10	57.9	671	233	232
30	174	2012	77.6	77.3
100	579	6708	23.3	23.2
300	1737	20120	7.76	7.73
750	4342	50310	3.1	3.09
1500	8684	100600	1.55	1.55

- Human PK profiles were predicted using a 1-compartment model with the projected human PK parameters for PF-07293893. The model assumes linear PK at all doses CCl ██████████ ██████████.
- Safety margins calculated using the total exposure limits in human which was based on unbound C_{max} (CCl ██████████ ng/mL) and unbound AUC_{24} (CCl ██████████ ng•h/mL) observed at NOAEL (100 mg/kg) in 1-m GLP toxicology study in mouse, the most sensitive species and corrected with human protein binding ($f_{u,p} = CCl$)

The PF-07293893 starting dose level of 10 mg is planned. The predicted PF-07293893 C_{max} and AUC_{24} after single dose of 10 mg are approximately 233- and 232-fold, respectively, below the exposure limit defined for PF-07293893 dose escalation in [Section 4.3.3](#). The maximum target coverage following a single 10 mg dose is predicted to be [CCI](#) % with [CCI](#) maximum increase in [CCI](#). The predicted PF-07293893 exposures (C_{max} and AUC_{24}) after single dose of 10 mg are approximately [CCI](#) lower than predicted exposures at projected human efficacious dose. A single dose of 1500 mg (the top dose in [Table 3](#)) is estimated to provide an exposure margin of [CCI](#) for both C_{max} and AUC_{24} relative to the exposure limits.

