- If, at any dose level, the average exposure reaches or exceeds the PK stopping limits, total C_{max} of **CCI** ng/mL or total AUC_{24} of **CCI** ng·h/mL. In addition, individual PK data, including the maximum exposure observed in individual participants within a cohort will be considered alongside the mean exposures for the cohort. The dose

escalation will be stopped if individual maximum exposure in ≥ 2 participants reaches or exceeds the PK stopping limits, total C_{max} of **CCI** ng/mL or total AUC_{24} of **CCI** ng·h/mL.

- If, based on the observed data, the group mean C_{max} or AUC (based on total plasma concentration) of the next planned dose is projected to exceed the escalation limits, that dose will not be explored. Modified doses may be explored if they are not expected to exceed PK stopping criteria.

Progression to the next dose will occur if the last dose was well tolerated and after satisfactory review of the available safety and PK data.

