9.3.2.1. Derivation of PF-07293893 PK Parameters

The plasma PK parameters for PF-07293893, following oral dose administration, will be derived from the plasma concentration-time profiles using standard noncompartmental methods as detailed in Table 4, as data permit. Actual PK sampling times will be used in the derivation of PK parameters. If actual PK sampling times are not available, nominal PK sampling times will be used in the derivation of PK parameters.

Table 4. Plasma PF-07293893 PK Parameters

Parameter	Definition	Method of Determination
AUC _{last}	Area under the plasma concentration-time profile from time 0 to the time of the last quantifiable concentration (C_{last})	Linear/Log trapezoidal method
AUC _{inf*}	Area under the plasma concentration-time profile from time 0 extrapolated to infinite time	$AUC_{last} + (C_{last}^*/K_{el})$, where C_{last}^* is the predicted plasma concentration at the last quantifiable timepoint estimated from the log-linear regression analysis
C_{max}	Maximum plasma concentration	Observed directly from data

Table 4. Plasma PF-07293893 PK Parameters

Parameter	Definition	Method of Determination
T _{max}	Time for C _{max}	Observed directly from data as time of first occurrence
t _{1/2} *	Terminal elimination half-life	Log(2)/k _{el} , where k _{el} is the terminal phase rate constant calculated by a linear regression of the log-linear concentration-time curve. Only those data points judged to describe the terminal log-linear decline will be used in the regression.
CL/F*	Apparent clearance	Dose/AUC _{inf}
Vz/F*	Apparent volume of distribution	Dose/(AUC _{inf} ·k _{el})
AUC _{last(dn)}	Dose-normalized AUC _{last}	AUC _{last} /Dose
AUC _{inf(dn)} *	Dose-normalized AUC _{inf}	AUC _{inf} /Dose
C _{max(dn)}	Dose-normalized C _{max}	C _{max} /Dose

*As data permits

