3.3.3. Transporter biomarkers (optional)

Transporter biomarkers (eg, [CCI](#)) will be analyzed if feasible and deemed necessary. The AUC_{24} and C_{max} of each transporter biomarker will be derived if applicable, where the analysis scale is ln.

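### Does the plan need to derive AUC24 for PF-07293893 because the exposure limit is written in it?

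*SAP*

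**What the plan says.** Protocol 4.3.3 sets two human exposure limits, one opening "The human PF-07293893 C_{max} limit is a total C_{max} of" and the other "The human PF-07293893 AUC_{24} limit is a total AUC_{24} of"; both figures are redacted. The same pair of measures recurs in three places:

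- Protocol 4.2 commits the design to it: "The highest anticipated C_{max} and AUC_{24} of PF-07293893 will not exceed the pre-defined human exposure stopping limits".
- Protocol 4.3.4 and Table 3 express each projected exposure and margin in it, starting from the lowest dose: "The predicted PF-07293893 C_{max} and AUC_{24} after single dose of 10 mg are approximately 233- and 232-fold" below the limit.
- Protocol 6.6.1 makes it a stopping criterion: "If, at any dose level, the average exposure reaches or exceeds the PK stopping limits". The criterion names total Cmax and total AUC24. It applies to the mean, and to individual values once at least two participants reach a limit.

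The derivation sections use a different list. Protocol 9.3.2.1 obtains the parameters "using standard noncompartmental methods as detailed in Table 4, as data permit". Protocol Table 4 holds AUClast, AUCinf, Cmax, Tmax, half-life, CL/F, Vz/F and dose-normalised AUClast, AUCinf and Cmax. SAP 3.2 introduces its own list with "The following plasma PK parameters as described in Table 2 will be determined". SAP Tables 2 and 3 repeat the protocol list, and SAP Tables 4 and 5 summarise it. AUC24 is an endpoint only for the optional transporter biomarkers, in SAP 3.3.3: "The AUC_{24} and C_{max} of each transporter biomarker will be derived if applicable".

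**The concern.** A limit stated in one measure and a parameter list stated in another invite a mismatch. AUClast runs to the last quantifiable sample, which may be as late as 72 h and may differ between doses and participants. AUCinf includes an extrapolated tail. Neither is the area from 0 to 24 h.

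On this reading, the final report would contain no observed AUC24 to compare with the projections in Protocol Table 3, and no observed AUC margin to the limit derived from the mouse NOAEL. A reader who put AUClast in its place would get the wrong margin. For a first-in-human study, whose data are meant to support further development, that would be an awkward gap.

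**Working it through.** **1. The plan's own figures.** Margin = limit / projected AUC24. The limit is redacted, so recover it as exposure × margin from Protocol Table 3.

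| Dose (mg) | Projected AUC24 (ng·h/mL) | Margin | Product |
|---|---|---|---|
| 10 | 671 | 232 | 155,672 |
| 30 | 2012 | 77.3 | 155,528 |
| 100 | 6708 | 23.2 | 155,626 |
| 300 | 20120 | 7.73 | 155,528 |
| 750 | 50310 | 3.09 | 155,458 |
| 1500 | 100600 | 1.55 | 155,930 |

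A single limit between about 155,430 and 155,630 ng·h/mL reproduces all six printed margins after rounding. The table is consistent, and it does rest on AUC24.

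**2. How far the planned AUCs lie from AUC24.** At 1500 mg, AUC24/Cmax = 100600/8684 = 11.58 h. The footnote to Protocol Table 3 names a one-compartment model. Half-life and absorption rate (ka) are redacted, so ka is assumed over a range and the elimination rate k is solved to match 11.58 h.

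- Instantaneous absorption: AUC(0–T)/Cmax = (1 − e^(−kT))/k. Matching at T = 24 gives a half-life of 9.85 h. Then AUC72/AUC24 = (1 − e^(−72k))/(1 − e^(−24k)) = (1 − 0.006)/(1 − 0.185) = 1.219.
- First-order absorption: AUC(0–T) is proportional to (1 − e^(−kT))/k − (1 − e^(−ka·T))/ka, with Cmax at t = ln(ka/k)/(ka − k).

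| Assumed ka (/h) | Half-life (h) | AUC72/AUC24 | 1.55 / ratio |
|---|---|---|---|
| instantaneous | 9.85 | 1.219 | 1.27 |
| 2 | 8.02 | 1.149 | 1.35 |
| 1 | 6.90 | 1.110 | 1.40 |
| 0.5 | 5.31 | 1.063 | 1.46 |
| 0.3 | 3.86 | 1.033 | 1.50 |

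AUCinf/AUC24 runs from 1.033 to 1.227 over the same range.

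**3. Direction of the error.** If the last quantifiable sample is at 24 h or later, AUClast is at least AUC24. An AUClast below the limit then proves that AUC24 is below it, and the margin is understated. AUCinf, where it can be estimated, bounds AUC24 from above in the same way.

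The error reverses only if quantifiable data end before 24 h. For example, with the last quantifiable sample at 12 h and instantaneous absorption, AUC12/AUC24 = 1/(1 + e^(−12k)). That is 0.889 for a 4 h half-life and 0.697 for a 10 h half-life.

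This is least likely where the margin is tight. With instantaneous absorption and a 4 h half-life, 24 h is six half-lives, so concentration falls by 2^6 = 64. The projected 24 h level is 8684/64 = 136 ng/mL at 1500 mg and 57.9/64 = 0.90 ng/mL at 10 mg. The assay limit is not given, but early loss of signal would appear first at the lowest dose. There a margin of 232 would read 232/0.697 = 333, and neither value is near the limit.

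**4. Who needs AUC24, and when.**

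| Use | Where AUC24 comes from |
|---|---|
| Stopping rule, mean and individual (Protocol 6.6.1) | The rule names AUC24, so applying it means computing it |
| Escalation review (Protocol 4.1 and 6.6; SAP 7.1) | PK through at least 24 h, reviewed after each period by unblinded sponsor staff |
| Any later comparison with the limit | SAP 6.2 lists all concentrations with nominal and actual times; the Schedule of Activities has samples on Day 1, at 24 h and on to 72 h |
| Secondary endpoint summaries | AUC24 is not an endpoint; the SAP list matches the protocol list |

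**The case for a change.** The strongest case for a change is that AUC24 carries the whole exposure argument of the protocol, and adding it would cost one more noncompartmental parameter from samples already taken. The other routes to it are loose:

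- SAP 7.1 calls the data reviewed after each period preliminary, and SAP 7.2 specifies no interim summaries.
- Protocol 9.3.2.2 allows further PK analyses but does not promise them in the study report.
- Tlast is listed but not summarised, so a summary of AUClast does not show the interval it covers.
- Samples after 10 h may be up to 1 h off nominal without counting as a deviation, and derivation uses actual times. A 0–24 h area therefore needs a convention for interpolation, and for a missing 24 h sample.

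The facts in this case stand: no final table of AUC24 is prespecified. The consequence does not follow. Interpolating to 24 h with the linear/log trapezoidal rule already named for AUClast is routine, and a missing 24 h sample can be handled in the same way from the neighbouring samples. No objective or endpoint asks for a final comparison with the limits or with the projections in Protocol Table 3. For repeat dosing, under the linear PK that table assumes, single-dose AUCinf already projects the steady-state area over a dosing interval, and AUCinf is planned. The 1.50 to 1.27 range measures a substitution that the plan nowhere prescribes.

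**Conclusion.** No change is needed. AUC24 is absent from every PF-07293893 parameter table, so the final tables contain no prespecified like-for-like summary against the AUC limit. That is a gap in reporting detail which the PK analyst fills in the ordinary course of the study, because the stopping rule cannot be applied without AUC24. Followed as written, the escalation decisions and all planned PK summaries remain sound, and no stated rule gives a wrong answer.

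The size attached to the concern is an AUC to 72 h of 1.03 to 1.22 times AUC24. It depends on a one-compartment model with linear PK and on assumed absorption rates from 0.3/h to instantaneous. A longer true half-life would widen the gap, still in the cautious direction while the last quantifiable sample is at or after 24 h. The conclusion that no change follows does not depend on that range. It rests on the wording of the stopping rule, the review of at least 24 h of PK before each dose decision, and the full listing of concentrations.
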